13.2 TBA-7371 Concentration-Effect Relationship

Spearman correlations, simple linear regressions and graphical visualizations will be used to summarize correlation between TBA-7371 AUC_{inf} , C_{max} , T>MIC and CFU counts on solid media culture. The SAS PROC CORR and PROC REG will be used to compute Spearman correlations and fit simple linear regression models. The slope with 95% confidence interval, as well as the R-squared will be reported for the simple linear regression. This will be reported by treatment group as well as overall.

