13.1 TBA-7371 Pharmacokinetics

Timing of TBA-7371 sampling for participants randomized to TBA-7371 will be as follows:

	QD Dosing	BID Dosing	TID Dosing
Screening Phase	Predose	Predose	Predose
Study Treatment Phase	
 Predose on Days 1, 2, 4, 7, and 14. 30 min, 1h, 2.5h, 3h, 4h, 6h, 7h, 10.5h, 12h, and 16.5h on days 1, 7, and 14. 	
 Predose on Days 1, 2, 4, 7, and 14. 30 min, 1h, 2.5h, 3h, 4h, 6h, 7h, 10.5h, and 12h on days 1, 7, and 14. 	
 Predose on Days 1, 2, 4, 7, and 14. 30 min, 1h, 2.5h, 3h, 4h, 6h, and 7h on days 1, 7, and 14.

TBA-7371 concentrations below the limit of quantitation will be set to 0. TBA-7371 concentrations will be summarized by treatment group using nominal time points for all participants in the PK population. The following descriptive statistics will be provided: N, arithmetic mean, standard deviation, arithmetic percent coefficient of variation (CV), median, minimum, maximum, geometric mean, and geometric percent CV. Linear and semi-log plots of individual and mean concentrations versus nominal time will be presented by treatment group. Plasma concentration of TBA-7371 having value 0 will be excluded from semi-log plots.

The following PK parameters of Days 1, 7, and 14 will be derived using non-compartmental model.

Day 1	Day 7	Day 14
C _{max} , T _{max} , C _{last} , T _{last} , AUC _{inf} , AUC _{last} , AUC _{tau} , C _{min} , half-life,	C _{max} , T _{max} , C _{last} , T _{last} , AUC _{inf} , AUC _{last} , AUC _{tau} , C _{min} , half-life, accumulation ratio (C _{max} of day 1/C _{max} of day 7)	C _{max} , T _{max} , C _{last} , T _{last} , AUC _{inf} , AUC _{last} , AUC _{tau} , C _{min} , half-life, accumulation ratio (C _{max} of day 1/C _{max} of day 14)

- C_{max} – maximum plasma concentration
- C_{min} – minimum plasma concentration
- T_{max} – time to maximum plasma concentration

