- λ_z – elimination rate constant. The elimination rate constant will be calculated as the negative of the slope of the terminal log-linear segment of the plasma concentration-time curve. The slope will be determined from a plot of the natural log of the terminal plasma concentrations against time; at least 3 terminal plasma concentration time points, beginning with the final concentration \geq LLOQ and not including C_{max}, will be selected for the determination of λ_z; the regression will have a coefficient of determination R² \geq 0.9000.
- Half-life – terminal half-life = ln(2) / λ_z.

- AUC_{last} – area under the plasma concentration-time curve from 0 up to the last measurable concentration \geq LLOQ. AUC is calculated using the linear trapezoidal method.
- AUC_{inf} – AUC extrapolated to infinity. $AUC_{inf} = AUC_{last} + C_{last} / \lambda_z$, where C_{last} is the last measurable concentration \geq LLOQ and λ_z is the terminal phase rate constant.
- AUC_{tau} – AUC to the end of the dosing period.

PK parameters of days 1, 4, 7, and 14 will be summarized using descriptive statistics number of participants, arithmetic mean, standard deviation, arithmetic percent CV, median, minimum, maximum, geometric mean, and geometric percent CV and will be provided by treatment group.

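### The pooled AUC–CFU correlation in SAP 13.2 uses AUCinf, which for BID and TID reflects one dose (plus carry-over after Day 1) and not daily exposure

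*SAP*

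**What the plan says.** Protocol 9.5 and Table 9 relate CFU response to AUC, Cmax and T>MIC without saying which AUC, and 9.5 does so for the treatment groups combined. SAP 13.2 narrows AUC to AUCinf: "Spearman correlations, simple linear regressions and graphical visualizations will be used to summarize correlation between TBA-7371" AUCinf, Cmax and T>MIC on one side and CFU counts on the other. It adds: "This will be reported by treatment group as well as overall". No profile day is given. SAP 13.3, by contrast, names Day 14 for its Cmax. SAP section 8 declares no changes to the planned analyses, so the choice of AUCinf is not explained.

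SAP 13.1 supplies the pieces:

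- "The following PK parameters of Days 1, 7, and 14 will be derived using non-compartmental model".
- AUCinf is "AUC extrapolated to infinity", computed as AUClast plus Clast divided by the terminal rate constant. No term removes drug left from earlier doses.
- AUClast is the "area under the plasma concentration-time curve from 0 up to the last measurable concentration" at or above the LLOQ.
- TID post-dose samples are at "30 min, 1h, 2.5h, 3h, 4h, 6h, and 7h on days 1, 7, and 14". BID samples run to 12 h and QD samples to 16.5 h. SAP Appendix 1, footnote 15, says that the 12 h BID sample and the 7 h TID sample are taken before the second daily dose.

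Doses are at 0 and 12 h for BID, and at 0, 7 and 14 h for TID. AUCtau is also derived on all three days but is not used in 13.2. The protocol's abbreviation list sets tau at 24 hours; SAP 13.1 takes AUCtau to the end of the dosing period.

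**The concern.** The CFU response builds up over days of dosing, so the matching AUC is the area over a full day. AUCinf never observes the second or third daily dose. Once the regimens are pooled, BID and TID participants sit too low on the exposure axis relative to QD participants, and both the Spearman coefficient and the regression slope are computed on that axis.

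This matters because protocol 4.3 includes the BID and TID arms to assess fractionating the daily dose, and Cohorts II and III are matched at 200 mg/day. An AUC that follows the single dose behaves much as Cmax does. The pooled analysis would then have little ability to separate activity driven by daily AUC from activity driven by peak. Protocol 4.2 says that the exposure–response relationship will guide regimen selection.

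**Working it through.** The plan states no figure for this correlation, so there is none to reproduce.

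**Inputs from the documents.** Regimens (protocol 4.1): 100 mg QD, 100 mg BID, 200 mg QD, 100 mg TID and 400 mg QD, giving 100, 200, 200, 300 and 400 mg/day. Dose times, sampling ends and the AUCinf formula are as above.

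**Assumptions.** Linear PK, with results in units of mg/CL. No half-life is given, so it is varied. Write k = ln 2 / half-life and D for the single dose.

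**Target.** The steady-state AUC over 24 h is daily dose/CL: 100 / 200 / 200 / 300 / 400, in the order 100 QD / 100 BID / 200 QD / 100 TID / 400 QD.

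**Day 1.** AUCinf = D/CL, which gives 100 / 100 / 200 / 100 / 400 at any half-life. BID is low by 200/100 = 2-fold and TID by 300/100 = 3-fold. TID (300 mg/day) falls below 200 mg QD.

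**Steady state.** AUCinf = (D + drug left before the morning dose)/CL. Summing the residuals of all earlier doses gives:

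- QD: D / (1 − e^(−24k))
- BID: D(1 + e^(−12k)) / (1 − e^(−24k))
- TID: D(1 + e^(−10k) + e^(−17k)) / (1 − e^(−24k))

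For example, at an 8 h half-life e^(−24k) = 0.125, e^(−12k) = 0.354, e^(−10k) = 0.420 and e^(−17k) = 0.229. So 100 QD = 100/0.875 = 114, BID = 135.4/0.875 = 155 and TID = 165.0/0.875 = 189.

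| Assumed half-life | 100 QD | 100 BID | 200 QD | 100 TID | 400 QD |
|---|---|---|---|---|---|
| 24 h AUC (target, any half-life) | 100 | 200 | 200 | 300 | 400 |
| 2 h | 100 | 102 | 200 | 103 | 400 |
| 4 h | 102 | 114 | 203 | 125 | 406 |
| 8 h | 114 | 155 | 229 | 189 | 457 |
| 12 h | 133 | 200 | 267 | 258 | 533 |
| 24 h | 200 | 341 | 400 | 472 | 800 |

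**BID against 200 mg QD.** The ratio is (1 + e^(−12k))/2: 0.51 at 2 h, 0.68 at 8 h and 0.85 at 24 h. It is below 1 at every finite half-life, although the daily doses are equal.

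**TID against 200 mg QD.** TID is lower when e^(−10k) + e^(−17k) < 1. The root is a half-life of about 13.2 h. Below it TID is misranked; above it the two are in the right order.

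**Carry-over.** For QD, steady-state AUCinf exceeds the 24 h AUC by e^(−24k)/(1 − e^(−24k)): about 2% at 4 h, 14% at 8 h and 33% at 12 h.

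**Check on the sampling grid.** A one-compartment oral model (absorption rate 1.5/h, assumed), sampled at the SAP times with the linear trapezoid and the tail taken from the last three points, gives 115 / 158 / 230 / 194 / 459 at steady state with an 8 h half-life. This agrees with the closed form.

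**Illustrative effect on ranks.** With 15 participants per regimen and an assumed 30% CV in clearance, the pooled Spearman correlation between AUCinf and the 24 h AUC averages about 0.67 on Day 1. At steady state it is 0.69, 0.78, 0.88, 0.92 and 0.93 at half-lives of 2, 4, 8, 12 and 24 h.

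**The case against.** The strongest reply is that this is one descriptive metric among three, in a secondary analysis with no success criterion. That stands. The by-group correlations do not mix schedules and so cannot misorder them. The QD cohorts keep their 1:2:4 spacing among themselves. The ANCOVA in SAP 11.1.1 does not use exposure, and the EC90 model in 13.3 uses Day 14 Cmax.

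A reader might infer that AUCinf decides whether exposure targets are pursued. Protocol 9.5 does not support that: it says only that further analysis may be performed if a correlation is seen, and it lists three metrics.

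A reader might also infer that 100 mg TID is certain to rank below 200 mg QD on Day 14. It is not. That needs a half-life under about 13 h, which the documents neither give nor exclude, and at 12 h the two are nearly tied (258 against 267). Nor do the illustrative rank correlations show a reversal of the exposure axis; they show attenuation.

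Finally, it can be said that a daily measure is already at hand in AUCtau. It is derived, but 13.2 does not use it. If tau is read as one dosing interval, a plain swap would not help: steady-state AUC0-12 for 100 mg BID is 100, the same as the 24 h value for 100 mg QD.

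**Conclusion.** The pooled AUC analysis in SAP 13.2 is wrong as specified. No half-life makes AUCinf equal daily exposure across these five regimens. Under linear PK two errors hold whatever the half-life: on Day 1, BID is understated 2-fold and TID 3-fold, with TID below 200 mg QD; at steady state, BID scores below 200 mg QD. The steady-state misranking of TID is conditional on a half-life below about 13 h. The unnamed profile day is part of the defect, because the size of the error depends on it.

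The consequence is confined to the overall AUC correlation and regression, which may inform later exposure-target work but do not settle it. The point is worth correcting before the analysis is run and is no threat to the primary result.

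**What to change.** In SAP 13.2, name Day 14 and replace AUCinf with a steady-state 24 h AUC. Reconcile tau between the protocol (24 h) and SAP 13.1 (end of the dosing period), and build the metric on the AUCtau already derived:

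- QD: AUC0-24, with the Day 14 pre-dose concentration standing in for the 24 h value to close the interval after the 16.5 h sample.
- BID: 2 × AUC0-12, stating the assumption that morning and evening exposure are equal.
- TID: a 24 h AUC by superposition or from a population PK model (listed in SAP 5.3 as a possible exploratory analysis). The 0–7 h area cannot simply be multiplied by 3, because the intervals are 7, 7 and 10 h.

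Under linear PK this restores 100 / 200 / 200 / 300 / 400 at every half-life. The cost is SAP wording and one derived parameter, with no new samples. The downside is that the TID value rests on a modelling assumption, which should be stated alongside the result.

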13.3 Exposure-Response Analysis

The exposure-response E_{max} model will be used to estimate EC_{90} as follows:

$$BA_{CFU}(0-14) = \frac{E_{max} \cdot C_{max(ss)}}{EC_{50} + C_{max(ss)}} + \varepsilon$$

where:

- $BA_{CFU}(0-14)$ is the average change in log(CFU) counts over each day from screening to day 14.
- E_{max} is the maximal TBA-7371 EBA effect.
- EC_{50} is the expected concentration of TBA-7371 associated with 50% of E_{max} .
- $C_{max(ss)}$ is the steady state C_{max} of TBA-7371 measured at day 14.
- ε is a random error assumed to be normally distributed with mean zero and constant variance σ^2 .

Exposure-response analysis will be performed in the PK population with participants having PK data measured on day 14. The SAS PROC NLMIXED procedure will be used to fit an E_{max} model. Maximum likelihood estimates and corresponding 95% CIs for E_{max} and EC_{50} will be provided. The prediction of EC_{90} to reach 90% of E_{max} is computed as

$$EC_{90} = 9 \cdot EC_{50}$$

95% CI for the estimate of EC90 will be provided. An exposure-response curve of E_{max} model will be produced and vertical reference lines for EC₅₀ and EC₉₀ will be provided for each treatment group as well as overall.

Alternative sigmoid exposure-response model may be explored if deemed appropriate.

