6.2 Sample Size Determination

Anticipating all cohorts are to be assessed in the study, approximately 90 participants will be randomized in a 5:1 ratio to either TBA-7371 or control group, totaling N = 15 participants for each TBA-7371 treatment and control groups (receiving treatment with HRZE).

Bactericidal effect

Based on Diacon et al. (Diacon, 2013) standard deviations associated with BAcfu(0-14) were relatively consistent across 5 treatment groups, ranging from 0.05 to 0.08. If we assume conservatively that the true standard deviation of the BAcfu(0-14) measures for the TBA-7371 treatment groups is equal to 0.1, then with N = 15 per group we have 80% (90%) power to detect a true group mean BAcfu(0-14) reduction of 0.067 (0.079), using a 1-sided alpha = 5%. For reference, the observed BAcfu(0-14) reduction in Diacon et al, 2013 were 0.040, 0.056, 0.077, 0.104, and 0.122 for Bedaquiline 100 mg, 200 mg, 300 mg, 400 mg and standard HRZE, respectively.

Safety

With N = 15 per group, we have approximately 80% (90%) probability to observe at least one AE if the true AE rate is 10% (15%). We have only 54% probability to observe at least one AE if the true AE rate is 5%. Across the five TBA-7371 treatment groups (N=75), we have 90% probability to observe at least one AE if the true AE rate is 3.0%.

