6.5 Pharmacokinetic Measures

Table 5. PK and PK/PD Endpoint

	Endpoint
Secondary PK and PK/PD	
● TBA-7371 concentration profiles and PK parameters over the 14-day treatment interval: C_{max}, T_{max}, C_{last}, T_{last}, AUC_{inf}, AUC_{last}, AUC_{tau}, C_{min}, half-life, accumulation ratios.● Correlation between TBA-7371 AUC, C_{max}, T>MIC and CFU counts on solid media culture.● Expected concentration associated with 90% of the maximal TBA-7371 EBA effect (EC90).

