Appendix 4 SAS Code

SAS code for computing 95% confidence interval for single proportion based on the mid-P method:

```
proc freq data=<dataset> order=freq;
  tables category / binomial (CL=MIDP) alpha=0.05;
  weight Count;
run;
```

SAS code for response-exposure E_{max} model:

```
ods output fitstatistics=<Data with aic>;
ods output parameterestimates=<Data with slope estimates>;
proc nlmixed data=<dataset>;
  by <treatment group>;
  parms Emax=<numeric>
    EC50=<numeric>
    s2=<numeric>;
  mu=(Emax*Cmax) / (EC50+Cmax);
  model <Avg. Slope(0-14)> ~ normal(mu,s2);
run;
```

SAS code for bilinear regression model with κ as one of the parameters:

```
ods output fitstatistics=<Data with aic>;
ods output parameterestimates=<Data with slope estimates>;
ods output additionalestimates=<Data with BA(0-14) estimate>;
run;
proc nlmixed data=<dataset>;
  by <subject ID>;
  parms alpha=4 to 8 by 0.5    betal=-0.3 to 0.3 by 0.05
beta2=-0.3 to 0.3 by 0.05    kappa=2 to 10 by 1    s2=0.05 to 0.3
by 0.05 / best=1;
  bounds alpha >0,    1 < kappa < 14,    s2>0; * Add constraints to
parameters to improve convergence;
  if day <= kappa then mu = alpha + betal*day;
  else if day > kappa then mu = alpha + betal*kappa +
beta2*(day-kappa);
  model logCFU ~ normal(mu,s2);
  estimate 'BACfu(0-14)' (kappa*betal + (t_last-
kappa)*beta2)/t_last; *Estimate BA(0-14);
run;
```

SAS code for bilinear regression model with kappa fixed at 2:

```
ods output fitstatistics=<Data with aic>;
ods output parameterestimates=<Data with slope estimates>;
proc nlmixed data=<dataset>;
  by <subject ID>;
  parms alpha=4 to 8 by 0.5    beta1=-0.3 to 0.3 by 0.05
beta2=-0.3 to 0.3 by 0.05 s2=0.05 to 0.3 by 0.05 / best=1;
  bounds alpha >0,    s2>0; * Add constraints to parameters to
improve convergence;
  if day <= 2 then mu = alpha + beta1*day;
  else if day > 2 then mu = alpha + beta1*2 + beta2*(day-2);
  model logCFU ~ normal(mu,s2);
run;
```

SAS code for simple regression model:

```
ods output fitstatistics=<Data with aic>;
ods output parameterestimates=<Data with slope estimates>;
proc nlmixed data=<dataset>;
  by <subject ID>;
  parms alpha=4 to 8 by 0.5    beta1=-0.3 to 0.3 by 0.05    s2=0.05
to 0.3 by 0.05 / best=1;
  mu = alpha + beta1*day;
  model logCFU ~ normal(mu,s2);
run;
```

SAS code for ANCOVA (lsmeans statement used to estimate 90% CIs, lsmestimate statements used for one-sided 5% p-values, trt = treatment group with HRZE as reference):

```
proc mixed data=<dataset>;

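### As coded, the 95% CI for EC90 is symmetric on the concentration scale: at the planning SD its lower limit is almost always negative, and its upper limit is too often too low if EC50 is at or above the 100 mg Cmax

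*SAP*

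**What the plan says.** SAP 13.3 models BA_CFU(0-14) as a hyperbolic Emax function of an exposure term that "is the steady state C_{max} of TBA-7371 measured at day 14". It promises 95% intervals for Emax and EC50, computes EC90 as 9 x EC50, and adds that "95% CI for the estimate of EC90 will be provided". No interval method is named. Reference lines for EC50 and EC90 on the fitted curve "will be provided for each treatment group as well as overall", so a pooled result is intended.

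Appendix 4 is the only place that shows how the interval would be obtained. The mean line begins "mu=(Emax*Cmax) / (EC50+Cmax", so EC50 enters as a plain concentration. The block has no BOUNDS line, no log parameter and no ESTIMATE statement for EC90. The free-node bilinear block in the same appendix has both a BOUNDS and an ESTIMATE statement. Results are captured with "ods output parameterestimates=<Data with slope estimates>". The Emax code runs only by treatment group; the pooled fit is in the text but not in the code.

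**The concern.** NLMIXED's parameter-estimates table gives estimate +/- t x SE by default, and multiplying by 9 keeps that symmetry. A hyperbolic curve needs a 9-fold rise in concentration to go from 50% to 90% of Emax. Three of the five regimens give 100 mg per dose, and the largest single dose is only four times that. EC50 is therefore weakly identified, with a long right tail. Low estimates also come with small standard errors, so the interval is shortest when the estimate is too low.

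EC90 is the secondary endpoint for the lowest exposure with maximal effect (SAP 5.2), and Protocol 4.2 says the exposure-response relationship will guide regimen selection. A negative lower limit cannot be interpreted. An upper limit that stops short understates the exposure that may be needed. This applies to the pooled fit, so it is a separate matter from fitting each regimen alone.

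**Working it through.** **Inputs from the documents.** 15 participants per regimen ("Across the five TBA-7371 treatment groups (N=75" in SAP 6.2); planning SD of BA_CFU(0-14) 0.1, and 0.05 to 0.08 in the cited study (SAP 6.2); the five regimens (Protocol 4.3); the model and code (SAP 13.3, Appendix 4).

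**Assumed, because the documents give no values.** Mean Cmax proportional to the single dose, so 1, 1, 2, 1, 4 in units of the mean 100 mg Cmax; between-participant CV 40%; true EC50 0.25 to 4 units; true effect at 400 mg QD 0.067 to 0.112 per day.

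**1. The plan's own figure.** Noncentrality is 0.067/(0.1/√15) = 2.595 and 0.079/(0.1/√15) = 3.060. A one-sided 5% t-test on 14 df then has power 79.4% and 89.7%, against the stated 80% and 90%. The SD is being read correctly. No operating figure is given for the EC90 interval.

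**2. When the lower limit is negative.** EC50 x (1 - t x RSE) < 0 when RSE > 1/t, where RSE is the SE divided by the estimate. With t = 1.992 on 75 df, that is RSE > 50.2%.

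**3. Expected RSE, one case by hand.** Take EC50 = 1 and 0.112 at 400 mg, so Emax = 0.112 x 5/4 = 0.14, and put every participant at the regimen mean. With f = C/(1+C) and g = -0.14 x C/(1+C)²:

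- C = 1 (45 participants): f = 0.500, g = -0.0350
- C = 2 (15): f = 0.667, g = -0.0311
- C = 4 (15): f = 0.800, g = -0.0224

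The sums are Σf² = 27.517, Σfg = -1.3674 and Σg² = 0.07717. At SD 0.1, Var(EC50) = 0.01 x 27.517/(27.517 x 0.07717 - 1.3674²) = 1.085, so SE = 1.04 and RSE = 104%. An interval centred on the truth would be 9 x (1 +/- 1.992 x 1.042) = -9.7 to 27.7, for a true EC90 of 9 and a highest regimen mean of 4.

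The SE scales with SD/Emax. SD 0.08 gives RSE 83%. SD 0.05 gives 52%, close to the threshold. SD 0.05 with Emax 0.20 gives 36%, below it.

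**4. Simulation of the pooled fit as coded** (N = 75, EC50 unbounded, 3,000 trials per scenario, limits x 9):

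| SD | Lower limit negative | Upper limit below true EC90 (nominal 2.5%) |
|---|---|---|
| 0.10 | 99.9-100% | 10.7-23.7% |
| 0.08 | 99.0-100% | 8.8-19.6% |
| 0.05 | 42.6-100% | 6.4-13.0% |

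At SD 0.1 coverage is 76-89%. With EC50 of 1 unit or more, the upper-limit miss is 11.6-23.7%. The case in step 3 gives 100% negative, 11.6% too low and 88.4% coverage. Misses in the other direction are at most 0.3%. Varying the CV (20-60%), using 13 per regimen, or assuming accumulation or more-than-proportional Cmax leaves at least 99.7% negative and 9.6-13.3% too low (SD 0.1, 0.112 at 400 mg).

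**5. Positive EC50 estimates only, SD 0.1.** With EC50 of 1 unit or more, the upper limit is too low in 3.8-16.5% of these fits. A smaller run (400 trials per scenario, CV 35%) gives about 5-19%, with 94-100% of lower limits negative. At EC50 0.25 units the upper-limit miss is 0-1.4% over all SDs.

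**6. Strong effect, low SD.** With Emax 0.20, SD 0.05 and EC50 0.5 to 2, negative lower limits fall to 2-9% in one run and about 5-20% in the other. The upper limit is still too low in 5-8%.

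**7. Alternatives.** Profile likelihood with EC50 > 0 covers 94.2-97.1%, with the upper limit too low in 0.1-3.3%. A Wald interval on log EC50 removes the upper-limit fault (0-0.2% at SD 0.1), but its lower limit lies above the truth in up to about 9% at EC50 0.25.

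**The case against.** - **The method is inferred.** SAP 13.3 names none, and the Emax code is a template with placeholders that covers only the per-regimen fit. A reader might infer that the SAP prescribes a Wald interval. It does not; a log-scale or profile interval would comply with its text. But the code is the only guidance given, and followed as written it yields the symmetric interval.
- **The rates are assumptions.** This stands. Protocol 4.3 suggests 200 mg QD or more may be needed, which favours a higher EC50; Protocol 2.3 allows an effect at 100 mg/day. The documents do not settle whether EC50 lies in the range where the upper limit fails.
- **Rates depend on which fits are kept.** In the positive-estimate run, up to about 31% of trials had no interior fit and were dropped. That is why figures are given both with EC50 unbounded and for positive estimates.
- **Dose range is not exposure range.** The model uses individual Cmax, which spans about 10- to 23-fold at CVs of 25-50%. This is fair, and the 4-fold dose range alone does not prove the point. The simulations use individual Cmax and still show the fault.
- **Extrapolation is visible.** A reader might infer that the plan hides an EC90 beyond the data. It does not, because the planned reference line would show it. A sigmoid alternative is also allowed.
- **Limited consequence.** No success criterion uses this interval, and the planned escalation reviews rest on safety and, where available, PK data.

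**Conclusion.** The point holds, with conditions. If Appendix 4 is followed, the pooled EC90 interval is symmetric on the concentration scale. At the planning SD of 0.1, its lower limit is negative in nearly all simulated trials. When EC50 is at or above the mean 100 mg Cmax, its upper limit is below the true EC90 in about 5-19% of positive-estimate trials and about 11-24% with EC50 unbounded, against 2.5%.

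A reader might infer that the interval fails whatever the truth. The calculations do not support that. In positive-estimate fits the upper-limit fault largely disappears when EC50 is well below that Cmax, and negative lower limits become uncommon at Emax 0.20 per day with SD 0.05. All rates rest on assumed Cmax, EC50 and Emax. The change should be made, but it concerns a secondary PK/PD endpoint and leaves the primary test untouched.

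**What to change.** In SAP 13.3 and Appendix 4:

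- Add code for the pooled fit.
- Parameterise on log EC50 or log EC90, for example EC50 = exp(lEC90)/9, so that EC50 stays positive.
- Name the interval as profile likelihood: the EC90 values whose deviance is within 3.84 of the minimum. With EC90 fixed the model is linear in Emax, so a grid of fixed values is enough.
- Show the upper limit as 'not reached' when the profile is unbounded.
- Mark EC90 as extrapolated when it exceeds the highest observed Day 14 Cmax.

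The cost is a few sentences and a short change to the code, with no new data. The interval will often be wider or open at the top: at SD 0.10, Emax 0.12 and EC50 1 to 4 units, the profile was unbounded above in 27-90% of simulated trials. That reflects how little such data can say about EC90.
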